Cardiac implantable electronic devices (CIED) are essential therapeutic tools for the management of arrhythmias in different clinical contexts (1, 2). Under the name of CIED are grouped pacemakers and cardiac defibrillators. Worldwide, more than 1 million implants of these devices are carried out annually (3). In Spain CIED implants are made in 230 centers, 4 most CIED are implanted in electrophysiology laboratories by electrophysiologist and the number of implants follows an increasing trend, being in the year 2015 the incidence of pacemaker first implantations/million inhabitants of 611 and that of defibrillators of 118 (5, 6).

A fundamental step in the implant procedure of a CIED is to establish a central venous access in order to insert the electrode catheters and place them in the cardiac chambers. In most procedures ($> 80\%$) it is accessed by the left axilo-subclavian axis, reserving the right side for left-handed patients or with vascular problems on the lefthand side. According to data from the European Heart Rhytm Association (7), 60% of implanters use as a preferential access vein cephalic, 20% axillary vein and 20% subclavian. In our midst, however, this proportion is quite different, with subclavian access being much more widespread.

The access route for the implant of a CIED has prognostic implications. Cephalic access has shown, in the short term, a null incidence of pneumothorax compared with the axillary or subclavian pathway, (8-10) because it does not require puncturing the subclavian region. On the other hand, in the medium and long term, when the access roads are compared, the subclavian approach has been related to a higher incidence of electrode problems as insulation defects and conductor fractures (11-13) which seems due to anatomical factors that condition the electrode's crush (14).

The technique of access through the cephalic vein for the implant of CIED has been carried out for more than five decades (15). Since it requires greater surgical dexterity, it was initially performed preferably by thoracic or cardiac surgeons. With the time, thanks to the technical improvements that have increased their percentage of effectiveness (16-22). However, the main problem for its universalization remains the

lack of knowledge of the technique on the part of many operators and an effectiveness of less than 85%.

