Two studies have compared the axillary vein against cephalic. The prospective and randomized study of Calkins H et al (32) compared the safety and efficacy of CIED implant by cephalic access to axillary access guided by venography. It found a higher percentage of success and shorter duration of the procedure by the axillary pathway and there were no differences in the rate of peri-procedural complications. The limitation of this study is that the use of an axillary venous access technique guided by venography limits its applicability and increases the possible complications of the technique. The prospective and randomized study of Squara F et al (33) compared the safety and efficacy of CIED implant by Cephalic access to axillary access guided by fluoroscopy and performed by physicians without any training in the technique. This particular study found no difference in success or complications with both techniques, although it was objective a shorter time to get venous access by axillary. Finally, the prospective observational study of Chan NY et A (113) analyzed the success rate and long-term electrode problems of the techniques of cephalic, subclavian and axillary access guided by venography. The success of cephalic access was significantly lower than the other two. After an average follow-up of 73.6 months, the problem-free survival of the electrode was significantly higher with axillary and cephalic access.

3) Justification.

The studies published so far demonstrate the superiority of the axillary and cephalic venous accesses against subclavian venous access in the CIED implant in terms of efficacy and safety. However, the most widespread venous access technique in our midst remains the subclavian pathway.

There are no recommendations from scientific societies on which access road should be the first choice, so the technique used is totally dependent on the experience and preferences of the implant physician.

To date, there are no studies comparing axillary and cephalic venous accesses performed with the most optimized technique by trained personnel.

4) Hypothesis.

- The axillary venous access pathway is superior in terms of efficacy to the cephalic access.
- The axillary venous access pathway is equal in terms of safety to the cephalic access.

5) Main objective.

To compare the efficacy and safety of fluoroscopy-guided axillary venous access to improved cephalic venous access in the cardiac stimulation device implant.

6) Secondary Objectives:

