- To compare the success rate of the accesses.
- To compare the duration of access procedures.
- To compare the duration of the implant according to the access.
- To compare the proportion of peri-procedural complications of the accesses.
- To compare the proportion of electrode problems at follow-up.

7) Methodology.

Design: randomized and open clinical trial in parallel groups.

Study population: The reference population is the patients who are implanted for the first time a CIED. The target population of the study will consist of patients who were first implanted with a CIED at the General University Hospital of Ciudad Real.

Selection criteria.

-Inclusion criteria: adults patients (>18 years old) with CIED implant indication at the General University Hospital of Ciudad Real who agree to participate in the study.

-Exclusion criteria: patients with one or more of the following characteristics:

- * pre-existing ipsilateral electrode,
- * ipsilateral lymphadenectomy,
- * cardiac resynchronization therapy indication.

Sample size and sampling procedure.

It is estimated that a sample size of 240 patients is needed for the study to have a 80% statistical power, an alpha value of 0.05 and taking into account the estimated losses due to lack of monitoring and/or data.

The selection of cases that will form the sample shall be conducted by consecutive sampling of all patients who are going to implant a CIED, meet the inclusion and

exclusion criteria, and give their consent to participate in the study. The cases will be allocated to each group (axillary venous access or cephalic venous access) by a procedure of 1:1 randomization by balanced blocks. Sealed envelopes with the number assigned to each of the subjects to be included will contain a card in which the type of venous access assigned will be required.

Period and scope of recruitment.

Patient recruitment will begin in september 2017 and continue until the required sample size is reached with an estimated time limit in december 2019.

Every patient, once recruited and performed the implant of the CIED, will be followed in the same way: before the discharge hospital with review of the device, the surgical wound and the chest X-ray and, later, ambulatory controls at 3, 6, 12 and 24 months of the Device and the generator bag.

The follow-up time will end with the completion of the study, but it may be sooner if the patient dies or moves from the hospital.

Variables:

1. Independent:

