Age, sex, hypertension, diabetes, dyslipidemia, obesity, type of heart disease, renal failure, COPD, CIED indication, type of implanted CIED, assigned access route, number of implanted electrodes, type of electrode implanted.

2. Dependents:

- Efficacy: success of assigned access, duration of the access technique, duration of the procedure, time of copying, cephalic canalization, axillary canalization, finally canalized route, main cause in case of failure.
- Safety: Complications of the procedure, Pneumothorax, hematoma, dislocation electrode, venous thrombosis, long-term electrode problems, insulation defect, driver's fracture, need for new electrode implant.

8) Phases of the project and Plan of work.

The research project will be carried out in the arrhythmia unit of the General University Hospital of Ciudad Real. The two investigators will be in charge of the recruitment of the patients, the implant of the CIED and the data collection. The principal investigator will be in charge of the analysis of the data. Advice and collaboration for analysis will be requested from the HGUCR Research support unit. The commencement of recruitment will be in the fourth quarter of 2017 and completion in the fourth quarter of 2019. No funding is necessary for the realization of the project.

9) Sources of information and data analysis.

The data for the study will be obtained from the patient himself (data of filiation and personal history), of the data collection sheet that will be filled during the implant and in the postoperative and the ambulatory monitoring of the device. All data will be entered in a database with SPSS software for further analysis.

The quantitative variables will be represented by means of the mean +/-standard deviation and the qualitative variables as percentages.

To evaluate the degree of adjustment to the normality of the quantitative variables will be used the test Kolmogorov-Smirnov.

The comparison between the two study groups will be done through an intention-to-treat analysis. The comparison of quantitative and qualitative variables will be carried out with the Student's t test. The comparison of quantitative and qualitative variables with the test of the U of Mann-Withney and the comparison of two Qualitative variables with the χ^2 test. A logistics linear regression analysis will be used for multivariate analysis.

A level of statistical significance shall be considered a value of $p < 0.05$.

10) Ethical aspects.

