- General ethical considerations:

The study compares two techniques of venous access for the implant of CIED that are perfectly described in the literature. Given the lack of rigorously compared to each other, there are currently no recommendations from scientific societies about which should be the first choice. Therefore, the decision to make one or the other depends fundamentally on the operator's preference and experience. Therefore, the impact on this patient population and the potential benefits derived from the results of an efficacy and safety study are important.

The prospective and randomized design of the study is justified by the greater scientific and methodological rigour that it involves.

The operators that will perform the study are perfectly trained in the realization of both techniques so that randomization will not cause any harm to the patient.

The investigators undertake to follow the procedures established by the Protocol and to inform and request the consent of all the participants. The institution is committed to ensuring the maintenance of assistance to the participants. Each of the Parties mentioned shall ensure the security and confidentiality of the identity of the subjects of the investigation.

The study will be conducted in accordance with the provisions of the Helsinki declaration (64th WMA General Assembly, Fortaleza, Brazil, October 2013).

- Information to participants:

The patients will be informed by the Investigator of the characteristics of the study and the possibility of inclusion in it. The acceptance of the patient to participate will be recorded in writing in the informed consent.

The subjects will be informed about the confidentiality of their identity and the registered clinical information that can only be reviewed by the authorized personnel.

11) Bibliography.

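### The equal-safety hypothesis is judged by intention-to-treat and a difference test alone; if cephalic access is the safer route and its failures are completed by puncture, this favours a finding of equality.

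*Combined protocol and SAP*

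**What the plan says.** Section 4 (Hypothesis) pairs a superiority hypothesis for efficacy with one of sameness for safety: "The axillary venous access pathway is equal in terms of safety to the cephalic access". No margin is attached.

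Section 9 (Sources of information and data analysis) gives one rule for both: "The comparison between the two study groups will be done through an intention-to-treat analysis". Binary outcomes are compared by chi-square at p<0.05. No per-protocol or as-treated analysis of safety is named.

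Section 7 (Variables) shows that failed access is foreseen. Its efficacy list includes success of the assigned access and "finally canalized route, main cause in case of failure". No safety analysis uses these items, and no section says which route follows a failed attempt.

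On rates, section 2 (Introduction) names as remaining obstacles to cephalic access "lack of knowledge of the technique on the part of many operators and an effectiveness of less than 85" per cent. It also states: "Cephalic access has shown, in the short term, a null incidence of pneumothorax compared with the axillary or subclavian pathway". It attributes this to the absence of a puncture in the subclavian region. Section 10 (Ethical aspects) says of this trial: "The operators that will perform the study are perfectly trained in the realization of both techniques".

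**The concern.** For a superiority claim, counting patients as assigned is the cautious choice, because crossover usually works against the claim. For a claim of sameness the same feature can work in its favour. A patient assigned to cephalic access whose electrodes finally go in by puncture brings the puncture risk into the cephalic arm. If cephalic access is the safer route, the arms then look more alike than the routes are.

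The two hypotheses are also linked. The more cephalic attempts fail, the better the efficacy hypothesis does and, under these conditions, the closer the safety result moves to the one predicted. A real excess of puncture-related complications could be reported as no difference, and the analysis as planned would not show that this had happened.

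**Working it through.** **Inputs.** Section 7 states that "a sample size of 240 patients is needed for the study to have a 80% statistical power", allocated 1:1, so 240/2 = 120 per arm before losses. The 240 cannot be reproduced, because endpoint, event rates, effect size and percentage lost are not given; only the arm size is used here. The documents give no overall complication rate for either route, so all complication rates below are assumptions, shown over a range.

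**Crossover.** Effectiveness below 85% means more than 15% failures. If that carried over to this trial, it would be more than 0.15 × 120 = 18 cephalic patients. The plan does not say that it does.

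**Dilution.** Let pC and pA be the cephalic and axillary complication rates, f and g the crossover shares in the cephalic and axillary arms, and let crossovers carry the risk of their final route. Then

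intention-to-treat difference = [pA(1−g) + pC·g] − [pC(1−f) + pA·f] = (pA − pC)(1 − f − g).

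- With g = 0 and f = 15%, 20%, 25%, the share kept is 85%, 80%, 75%.
- With g = 5%, it is 80%, 75%, 70%. A 3.0-point route difference becomes 2.40, 2.25, 2.10 points.

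**Chance of p≥0.05.** Exact binomial enumeration, 120 per arm, chi-square without continuity correction, g = 0:

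| Cephalic vs axillary rate (assumed) | f = 0 | f = 15% | f = 25% |
|---|---|---|---|
| 0% vs 2% | 78% | 84% | 88% |
| 0% vs 3% | 51% | 69% | 78% |
| 0% vs 5% | 14% | 48% | 63% |
| 2% vs 5% | 78% | 84% | 87% |
| 5% vs 10% | 68% | 76% | 81% |
| 5% vs 15% | 24% | 42% | 54% |

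At f = 15% the increase is 6 to 34 points. The effect does not depend on f reaching 15%: for 0% vs 5%, f = 5% already gives 27%.

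**The opposite direction.** Suppose both routes carry the same risk p, and a failed cephalic attempt adds e. The cephalic arm then has p + f·e against p. With p = 5%, e = 5 points and f = 15%, that is 5.75% vs 5%. The arms separate by 0.75 points, away from equality.

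**What a per-protocol set would add.** Take g = 5%, so 114 axillary patients, and f = 15%, 20%, 25%, so 102, 96, 90 cephalic patients. Assume that exclusion is unrelated to risk. Chance of p≥0.05:

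| Cephalic vs axillary rate (assumed) | Intention-to-treat | Per-protocol |
|---|---|---|
| 0% vs 3% | 72%, 76%, 80% | 74% each |
| 0% vs 5% | 52%, 60%, 66% | 32% each |
| 5% vs 15% | 46%, 52%, 58% | 30%, 33%, 34% |

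**Precision.** With equal 5% rates, the 95% half-width by intention-to-treat is 1.96 × √(2 × 0.05 × 0.95/120) = 5.5 points. With 114 and 102 patients it is 1.96 × √(0.05 × 0.95 × (1/114 + 1/102)) = 5.8 points.

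**The case against.** The strongest reply is that intention-to-treat is the right safety comparison here. Sections 3 and 10 ask which access should be the first choice. Complications of a rescue access are then a real consequence of starting with the cephalic vein, and counting them there is not bias. This stands, and it is why intention-to-treat should remain the main analysis. It does not settle the matter, because the hypothesis in section 4 is worded about the access pathway, and electrode problems during follow-up may plausibly depend on the vein that the electrode occupies.

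A reader might infer from "an effectiveness of less than 85" per cent that the sponsor expects at least 15% cephalic failures in this trial. The documents do not support that. The figure describes the technique in general, beside a remark on operators who do not know it. This trial uses an improved technique and trained operators, and section 2 also cites a randomised comparison that found no difference in success. That failures would be completed by puncture is likewise an inference. The nil cephalic rate concerns pneumothorax only; haematoma, dislodgement, thrombosis and lead failure are also on the safety list.

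Two further replies have force. First, the missing margin and low power are the larger source of a false finding of equality: 2% vs 5% is non-significant 78% of the time with no crossover at all. Second, a per-protocol set gains little in some scenarios, such as 0% vs 3%, and two non-significant results would agree without showing anything. This limits what the added set can do and rules out agreement of p-values as a criterion. It does not make the set useless, as the other two scenarios in the per-protocol comparison show.

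**Conclusion.** The point holds in conditional form. The plan tests a hypothesis of sameness with one analysis set and a difference test, and makes no safety use of the route finally used, which it records. If cephalic access is safer and cephalic failures are completed by puncture at the axillary risk, intention-to-treat keeps about 85% to 75% of the route difference at 15% to 25% cephalic crossover, and the chance of a non-significant result rises in every scenario tested.

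A reader might go further and conclude that intention-to-treat is wrong for safety, or that crossover must pull the arms together. Neither follows. Intention-to-treat answers the first-choice question validly. If failed attempts add complications and the routes are equally safe, the arms move apart. Intention-to-treat alone cannot tell dilution, added risk from failed attempts and true equality from one another. The sizes rest on assumed complication rates, on a crossover range that the plan does not state for this trial, and on 120 analysed patients per arm.

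**What to change.** In section 9:

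- Keep intention-to-treat as the main analysis for both hypotheses.
- For safety, report the risk difference with its 95% confidence interval in place of reliance on a non-significant chi-square test. Name an interval method that behaves with zero or few events.
- Add a supportive per-protocol set: patients with all electrodes placed by the assigned vein, identified from the recorded final route. State how patients with electrodes through two veins are classified.
- Add a table of complications by assigned and final route.
- Do not claim equal safety from p≥0.05 in either set. Base any such claim on whether both confidence intervals exclude a difference that the sponsor states in advance as important. Otherwise report that no difference was shown, with the interval.

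The cost is a few sentences, one added analysis and one table, from data already planned. Fixing this in advance matters because the trial is open and the principal investigator analyses the data (sections 7 and 8).

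The downsides are real. The per-protocol set is smaller, is not protected by randomisation and omits the complications of failed attempts, so it supports intention-to-treat and does not replace it. With half-widths near 5.5 to 5.8 points at a 5% rate, the trial may be unable to exclude the difference the sponsor names; the report should then say so.

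### Section 9 has no rule for an arm with no events: ordinary logistic regression on pneumothorax could then give an unusable adjusted odds ratio that conflicts with the planned chi-square test

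*Combined protocol and SAP*

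**What the plan says.** Section 9 plans three things that matter here.

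- The arms are compared as assigned: "The comparison between the two study groups will be done through an intention-to-treat analysis".
- Binary outcomes are tested without adjustment: "the comparison of two Qualitative variables with the χ^2 test". No exact test is named.
- The adjusted analysis is one sentence: "A logistics linear regression analysis will be used for multivariate analysis". It does not name the outcomes or covariates, choose between Wald and likelihood-ratio inference, or say what happens when an arm has no events.

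The list of variables in section 7 puts assigned access route among the independent variables. Among the dependent safety variables it lists "Complications of the procedure, Pneumothorax, hematoma, dislocation electrode, venous thrombosis". Section 2 (Introduction) says of earlier studies: "Cephalic access has shown, in the short term, a null incidence of pneumothorax compared with the axillary or subclavian pathway". It attributes this to the absence of a puncture. Section 4 hypothesises that the two routes are equally safe.

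**The concern.** Maximum-likelihood logistic regression has no finite estimate for a binary factor when one of its levels has no events. The coefficient grows with each iteration and its standard error grows faster. The Wald p-value therefore drifts towards 1 however large the excess in the other arm. Having few covariates does not help, because the problem arises with access route as the only term.

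The background in section 2 makes an empty cephalic arm a foreseeable result for pneumothorax. If that outcome goes into the model, the report could show an adjusted p near 1 beside an unadjusted p well below 0.05, and the plan does not say how to read the pair. The spurious value would also lean towards the equal-safety hypothesis in just the case where every event falls in the axillary arm.

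**Working it through.** **Inputs.** Section 7 gives 240 patients allocated 1:1, so 120 per arm. The 240 itself cannot be reproduced, because no endpoint, event rates or loss rate are stated; it is used here only for the arm size. The axillary pneumothorax count is not given and is varied as an assumption. Tests are taken as two-sided.

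**Step 1. The ordinary model at 0/120 cephalic versus 6/120 axillary.** Route is the only term.

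- After 15 Newton iterations: coefficient 13.26, SE 301, Wald p = 0.965.
- After 20 iterations: coefficient 18.26, SE 3,669, z = 18.26/3,669 = 0.005, Wald p = 0.996.

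The values depend on when the software stops, so none of them is an estimate. For any axillary count from 2 to 12 the Wald p after 20 iterations is 0.996. Adding three simulated covariates leaves it at 0.996.

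**Step 2. Other methods on the same 0 versus 6.**

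- Pearson chi-square: 240 × (6 × 120 − 114 × 0)² / (120 × 120 × 6 × 234) = 6.15, p = 0.013.
- Likelihood ratio from the ordinary model: 2 × [6 ln(6/120) + 114 ln(114/120) − 6 ln(6/240) − 234 ln(234/240)] = 8.47, p = 0.004.
- Firth logistic regression: with one binary term this adds 0.5 to each cell, so OR = (6.5 × 120.5)/(114.5 × 0.5) = 13.7; penalised likelihood-ratio p = 0.012.
- Risk difference: 6/120 − 0/120 = 5.0 points, score 95% CI 1.8 to 10.5.

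**Step 3. Across counts.**

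| Axillary vs cephalic events | Wald | Likelihood ratio | Pearson | Fisher | Firth |
|---|---|---|---|---|---|
| 4 vs 0 | 0.996 | 0.018 | 0.044 | 0.122 | 0.053 |
| 6 vs 0 | 0.996 | 0.004 | 0.013 | 0.029 | 0.012 |
| 8 vs 0 | 0.996 | 0.0007 | 0.004 | 0.007 | 0.003 |
| 8 vs 1 | 0.045 | 0.011 | 0.017 | 0.036 | 0.018 |

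A single cephalic event restores an ordinary fit. The expected event count per arm is half the total, so it is below 5 whenever there are fewer than 10 events. At 4 versus 0 this matters: Pearson falls below 0.05 and Fisher does not.

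**Step 4. How likely is the breakdown?** Section 2 puts the effectiveness of cephalic access below 85%. Taking 15% of 120, assume that 18 cephalic-assigned patients end with a puncture route and that only punctured patients can have a pneumothorax. At puncture rate p, the chance of no cephalic-arm event is (1 − p)^18. The chance of at least one axillary event is 1 − (1 − p)^120.

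| Assumed p | No cephalic event | At least one axillary event | Both |
|---|---|---|---|
| 1% | 0.83 | 0.70 | 0.58 |
| 2% | 0.70 | 0.91 | 0.63 |
| 5% | 0.40 | 0.998 | 0.40 |

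The chance of no cephalic event together with six or more axillary events is much smaller: 0.1%, 2.4% and 22% at the same three rates.

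**The case against.** A reader might infer that the trial would miss a real excess of pneumothorax. The documents do not support that. The secondary objective in section 6 compares proportions of complications, section 9 assigns such comparisons to chi-square by assigned arm, and that test falls below 0.05 from 4 versus 0 upwards. This part of the objection stands in full.

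A reader might also infer that the protocol predicts an empty cephalic arm. It does not. Section 2 reports literature on the route actually used. Under intention-to-treat, a patient assigned to cephalic access who is then punctured stays in the cephalic arm, and section 7 foresees this by recording the route finally used. An empty arm is plausible, not certain.

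Three further points narrow the concern. The plan never says that pneumothorax will be modelled. A p near 1 belongs to the Wald test, which the plan does not specify, and the likelihood-ratio test remains valid. A coefficient of 18 with a standard error of 3,669 is also recognisable as a failed fit, and section 8 foresees help from the research support unit. What remains is that the plan gives no instruction for that moment, and that the odds ratio and its Wald interval are unusable whichever test is chosen.

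The same failure could affect access success if no axillary access failed, but only at very high assumed success: the chance in 120 patients is 0.99^120 = 30% at 99% and 0.98^120 = 9% at 98%. This is a weaker example.

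**Conclusion.** The point holds as a weakness of the secondary, adjusted analysis. If pneumothorax is modelled by ordinary logistic regression and the cephalic-assigned arm has no events, the adjusted route effect cannot be estimated and its Wald p is about 0.996, against p = 0.013 from the planned chi-square at 0 versus 6. The condition has a 40% to 63% chance of arising, given 18 crossovers and the assumed puncture pneumothorax rates of 1%, 2% and 5%. The particular 0 versus 6 contrast is uncommon at the lower rates. The result rests on 120 per arm, on pneumothorax being among the modelled outcomes, and on Wald inference being reported. The main comparison is not affected, although its chi-square also needs an exact alternative for small counts. The change is worth making because it is cheap.

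**What to change.** In section 9, name the binary outcomes and covariates for the adjusted analysis, then add: *For any adjusted binary outcome with no events or no non-events in an arm, or with few events, the model is fitted by Firth penalised-likelihood logistic regression with profile-likelihood confidence intervals and p-values; Wald p-values are not reported. The unadjusted risk difference is given with a score 95% confidence interval. Fisher's exact test replaces chi-square when any expected count is below 5.* The sponsor should put a number on few events before looking at the data. Ordinary logistic regression can stay for outcomes that are not sparse.

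The cost is wording and a different fitting routine, with no new data or patients. Fisher's test is somewhat more conservative: at 4 versus 0 the p-value moves from 0.044 to 0.122.
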